Biomarker and Safety Study of Clozapine in Patients with Benign Ethnic Neutropenia (BEN)

08/27/2019
NCT02404155

Biomarker and Safety Study of Clozapine in Patients with Benign Ethnic Neutropenia (BEN)

Introduction:

Current monitoring guidelines for treatment with the medication clozapine have cut off values for white blood cell (WBC) counts that were based on Caucasian populations and do not take into account lower white blood cell counts and lower fluctuations seen in people of African descent. This leads to many people of African descent not receiving appropriate care with clozapine. This study will examine clozapine safety in patients of African descent with a history of a low absolute neutrophil counts (ANC), known as Benign Ethnic Neutropenia (BEN). Normal patterns of week-to-week fluctuations in ANC levels in individuals of African ancestry with BEN are not known, and no published research has examined variation in genes in African ancestry clozapine-treated patients with BEN. Conducting such research will generate genetic marker and safety data that could be used to expand access to clozapine for African American patients who otherwise are eligible to receive this superior treatment option.

We have recently been funded by NIMH to study clozapine in this population. We are working closely with the Food and Drug Administration (FDA) and have obtained an Investigational New Drug (IND) approval for the project.

This protocol outlines the details for an open label prospective study of six months of open label clozapine treatment that follows a six week period of WBC count monitoring to establish baseline values. It also contains the modified monitoring guidelines that will be used in BEN patients throughout the study. MPRC will be the coordinating site and will be the initial site to be IRB approved and running. Subsequently, we will also include Howard University and the Federal Neuropsychiatric Hospital Yaba, Lagos, Nigeria.

Background:

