New knowledge is needed to reduce this healthcare disparity and care gap for African-American patients who would otherwise benefit from clozapine treatment. To generate this knowledge, the objectives of the study are:

Aim 1: To study and understand the normal pattern of white blood cell fluctuations in BEN patients. We will study 250, mostly African ancestry, patients to determine the fluctuations of within-participant WBC and ANC (mean, S.D., frequency and duration of episodes of mild, moderate or severe neutropenia), measured weekly over a period of (up to) 6 weeks

Hypothesis:

BEN patients will have lower mean ANC and WBC than normal values reported in the literature. The normal variation in ANC and WBC will create sporadic episodes with ANC below guidelines in BEN patients.

Aim 2: To test to see if people with BEN have a genetic risk that may put them at risk of having a naturally lower WBC count than people who are White. We will establish ANC and WBC patterns in both those with and without the *DARC* allele.

We will also genotype a panel of variants in the human leukocyte antigen (*HLA*) complex gene recently shown to be associated with agranulocytosis in Caucasian patients, to explore the prevalence of co-occurrence of these *HLA* variants and the *DARC* null genotype in BEN patients, which might increase risk of agranulocytosis in AA and SSA participants with BEN. We anticipate that the high risk *HLA* variants will be in very low frequency in the AA and SSA population

*Hypothesis: Patients with the *DARC* null allele genotype will have lower ANC and WBC than people without the *DARC* null allele genotype.*

Aim 3: To test the safety of clozapine treatment in people with BEN. We also will study the normal fluctuations of WBCs and ANCs during 6 months of clozapine treatment. We will study the risk of potential episodes of agranulocytosis or serious infection. We will develop an upper 95% confidence interval for risk of agranulocytosis ($< 500 \text{ cells/mm}^3$), which may be compared to the known 1% agranulocytosis risk in European ancestry populations treated with clozapine. We will also estimate the risk of serious infection in clozapine-treated BEN patients.

Hypothesis 1 (DARC null allele patients):

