Current treated or untreated cancer*
Documented nutritional deficiencies (such as Beriberi, Pellagra, Rickets, Scurvy, Keshan Disease)*

*exclusion criteria for giving clozapine to neutropenic patients are similar to exclusion criteria for giving chemotherapy to BEN patients.

Smokers are permitted. All sites will pay careful attention to hospital admissions in smokers to ensure that the change in smoking status does not affect clozapine blood levels. Smoking is permitted at the hospital sites and blood levels should be drawn at the time of inpatient/outpatient change. This is just an extra precaution to ensure that changes in the amount and routine of smoking do not have large effects on clozapine optimization in these patients.

STUDY DESIGN AND METHODS:

- This is a single treatment group, open-label, prospective study. This study will take place at three sites; the Maryland Psychiatric Research Center (MPRC), University of Maryland School of Medicine, Howard University, and the Federal Neuropsychiatric Hospital Yaba, Lagos, Nigeria (FNPHY). The study will begin at the MPRC site and the other sites will come on board only when the studies and consents are fully approved at each site. We will notify the UMB IRB when each site is fully functioning.
- MPRC will be the lead site for regulatory compliance, coordination, design, leadership, data storage and analysis. The Nigerian site and Howard University both are well established research sites with ongoing NIH research and an enriched environment for clinical research. Patients will be enrolled for 9 months duration from a cohort of 250 African ancestry (African-American or Nigerian) subjects who have had evidence of neutropenia (ANC<2500 cells/mm³) in the past 24 months and are otherwise clozapine eligible.
- We will enroll a target of approximately 80 at MPRC, approximately 130 in Nigeria and approximately 40 at Howard University with a range of 70-90 at MPRC if needed, a range of 130-150 if needed in Nigeria and 40-50 at Howard if needed.

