- All participants will be recommended to undergo 6 weeks of weekly monitoring for ANC and WBC fluctuations and clinical evaluations. This may be fewer if the PI or treatment team feel waiting to begin clozapine would not be in the best interest of the patient. At least one week of observation is needed. This could also go longer if a patient is enrolled and clozapine start is delayed for a short period. After this period, subjects still meeting eligibility criteria will be treated for 6 months with open label clozapine with weekly WBC/ANC

monitoring. We will minimize the burden of assessments to focus on safety and retention and in order to simulate treatment as usual in a naturalistic design.

- Assessments: A full schedule of events is included below. At baseline, all participants will have a standard medical workup including a physical examination, Body Mass Index (BMI) measurement, and EKG (In USA only). Blood will be collected for complete blood count (CBC), Chemistry 14 panel with fasting blood glucose, lipid panel, HIV, thyroid panel, and liver function tests. Additional blood smear analyses for malaria parasites will be performed at FNPHY. A description of the time points for all of the assessments and laboratories are included in the schedule of events.

SCHEDULE OF EVENTS	Visit 1 Screening	Visit 2-5 (Pre-clozapine)	Visit 6 (Week prior to Clozapine start	Visit 7-30
Medical and Psychological evaluation	X			
Demographic information	X			
Inclusion/Exclusion criteria documentation	X			
SCID and DDF form	X			
Smoking status, Fagerstrom Test for Nicotine Dependence (can be done at visit 1 or 2-5)		X		
Blood draw for genotyping (one for storage and one for named genes)	X			
Cytokines (US only)		X		X (2 times) Visit 18 and 30)
Documentation of previous ANCs	X			
Consent and patient monitoring form	X			
HIV testing	X			
Concomitant medication list		X (weekly)	X	X (weekly)
ANC signoff each week		X (weekly)	X	X (weekly)
Blood smear for malarial parasites (Nigerian site)	X	X (every 2 weeks)	X	X (every 2 weeks)
Education/reminder on reporting infection	X	X	X	X (weekly)
Medical record review	X			

CBC with differential	X	X (weekly)	X*	X (visit 7-10 and 30)*
WBC/ANC finger stick**			X	X (weekly) until week 4 then optional thereafter
Chemistry 14 including lipids, liver enzymes, thyroid function, FBG, electrolytes	X		X	X (monthly) Visits 10,14,18,22,26,30)

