- All WBC with 3 to 5 part differential (by capillary and/or venous, respectively) will be obtained at the same time at each drawing when possible (approximately 9am to 12 pm) to avoid the confound of morning pseudoneutropenia and will be performed weekly for 6 weeks prior to clozapine and 6 months after clozapine. In participants who discontinue clozapine during the trial, weekly WBC/ANC measurements will be performed for an additional 4 weeks. The WBC and ANC at the two US sites will be performed by Lab Corp, which is fully licensed by the State of Maryland. The Laboratories Unit of the Maryland Department of Health and Mental Hygiene licenses laboratories and is responsible for ensuring federal certification of all laboratories located in Maryland, including federal certification in the Clinical Laboratory Improvement Amendments of 1988 Program, required for all clinical laboratory testing sites used in analysis of samples from US patients. WBC and ANC counts are calculated by automated cell counter by Lab Corp or by using The Athelas One lab using the Automated Haematology Analyzer .
- WBC and ANC at the Nigeria site will be performed in the well-equipped FNPHY Medical Laboratory using the Beckman Coulter (3 to 5 part differential) for automated counts with use of a microscope for manual WBC backup, under the direct oversight of [name], Head Medical Lab Technician. This laboratory routinely performs CBCs, is registered by the Medical Laboratory Sciences Council of Nigeria, the body for registration of diagnostic labs in Nigeria, and will abide by all requirements that are indicated when analyzing samples from Nigerian patients.
- WBC and ANC cutoff and reference criteria used for safety monitoring for clozapine are standardized in this protocol, so using different laboratories for these measurements are not of concern.
- If morning neutropenia occurs the afternoon (12-4pm) draw time is acceptable. The draw time will be documented.

Clozapine Blood Levels:

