We will also collect data on WBC, ANC and demographic information on people previously treated in Maryland on a waiver system. Their data is available in clinical charts at Spring Grove Hospital and will only collect with approval from the hospital and the Spring Grove Research Committee. These patients will not be eligible to reenroll in this study but the data will be available to add to the study as it will help decrease the final sample size needed to enroll in the study. We will link this data from another study approval where a waiver of informed consent has been granted to study antipsychotic use (HP-00040084).

PRIMARY OUTCOME VARIABLES:

The primary outcomes are to measure ANC levels, side effects and patient safety.

STATISTICAL ANALYSES:

Analysis of Effect of clozapine on WBC and ANC levels: We will characterize variation of WBC and ANC levels in participants by *DARC* null genotype. We anticipate 212+ AA participants with BEN who are homozygous for the *DARC* null allele who will be the focus of this analysis, with other participants with BEN to be examined in a separate analysis. We will compute within-patient means and standard deviations of weekly WBC and ANC by three months intervals, starting with the three-month pre-treatment phase, and continuing for the six-months of follow-up on clozapine treatment, and observe the frequency of ANC values observed that exceed specific levels of concern (e.g. <500, <700, <1000 cells/mm³). We will estimate the change from baseline in overall average WBC and ANC during each three month interval after initiation of clozapine, and assess whether these change with time using a mixed model for repeated measures ANCOVA, controlling for baseline. Frequency of other events of concern (serious infection, need for treatment for very low ANC) will also be reported. We will also perform analyses of effects of mean participant pre-treatment ANC, clozapine dose and clozapine blood level on mean ANC during clozapine treatment and ANC<500 cells /mm³ during clozapine treatment, using linear and logistic regression. To date all published work and US guidelines are based on non-BEN samples and not specific to schizophrenia patients.

For the study when we report the results we will evaluate a subgroup of people with a history of ANC < 1500 cells/mm³

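### The ANC/WBC interval analysis starts from a three-month pre-treatment phase that the design does not have, and does not say which draws count, so the lead-in and on-clozapine summaries are not like for like

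*Combined protocol and SAP*

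**What the plan says.** **Analysis.** Under STATISTICAL ANALYSES (Analysis of Effect of clozapine on WBC and ANC levels), per-patient means and SDs of weekly counts are computed for each three-month interval, "starting with the three-month pre-treatment phase, and continuing for the six-months of follow-up on clozapine treatment". The same sentence adds a frequency of ANC values at levels of concern, with 500, 700 and 1000 cells/mm³ as examples. A repeated-measures mixed model then estimates change from baseline in average ANC and WBC. No minimum number of baseline values is set, and no rule says which draw represents a week.

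**Lead-in.** The Introduction describes "six months of open label clozapine treatment that follows a six week period of WBC count monitoring to establish baseline values". Aim 1 has counts "measured weekly over a period of (up to) 6 weeks". STUDY DESIGN AND METHODS says "All participants will be recommended to undergo 6 weeks of weekly monitoring for ANC and WBC fluctuations and clinical evaluations", allows a shorter period ("At least one week of observation is needed") and adds "This could also go longer if a patient is enrolled and clozapine start is delayed for a short period". LABORATORY MONITORING says that counts "will be performed weekly for 6 weeks prior to clozapine and 6 months after clozapine". PARTICIPANT COMPENSATION gives about 8 visits or fewer in the first 6 weeks, about 24 in the last 6 months, and about 8 months in all. One statement in STUDY DESIGN AND METHODS points elsewhere: "Patients will be enrolled for 9 months duration from a cohort of 250 African ancestry" subjects.

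**Extra draws.** In the MONITORING GUIDELINES table, an on-treatment ANC of 500-999 leads to a redraw and twice-weekly draws, and one below 500 to daily draws. The schedule footnote and the section on WBC and infection monitoring tie closer monitoring to 1200 instead. The main initiation route requires two baseline values of at least 1000.

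**The concern.** The first interval of the analysis cannot be built as written, because most participants will have about half of it. Three consequences follow.

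- The expected per-patient SD depends on how many serially correlated values enter it, so a short baseline block gives a smaller SD than a longer on-treatment block from the same process.
- Extra draws happen because a value was low, and they fall mostly on clozapine. If they are counted, low values are over-represented on treatment.
- If the lead-in is very short and must contain two values of at least 1000, baseline is high by selection, and later values drift down without any drug effect.

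Aims 1 and 3 describe ANC fluctuation before and during clozapine, and the section on the importance of the knowledge to be gained relies on a pretreatment comparison. All three artefacts make clozapine look more destabilising or more neutropenic than it is.

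**Working it through.** **1. Durations.** Three plus six months is 9 months, which matches only the enrolment duration in STUDY DESIGN AND METHODS. Six weeks plus six months is 6/4.345 + 6 = 7.4 months, which is compatible with the approximate 8 months under PARTICIPANT COMPENSATION. The payment there also fits: (8 + 24) visits × $20 = $640, the stated total. The schedule has Visits 1-6 before clozapine and Visits 7-30 on it. That is about 6 baseline values (up to about 8 visits) against 24/2 = 12 per on-treatment interval. A three-month lead-in would hold about 13.

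**2. Assumptions for steps 3-5.** The documents give no within-patient ANC variability. I assumed log-normal weekly ANC with first-order autocorrelation, within-patient CV 20-30%, 10% draw noise and no drug effect.

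**3. Per-patient SD.** For independent normal values E(s) = c4(n)·σ, with c4 = 0.798, 0.952 and 0.978 for n = 2, 6 and 12. The ratio is 0.978/0.952 = 1.03 for 12 against 6 values, and 0.978/0.798 = 1.23 for 12 against 2. With weekly correlation ρ, E(s²) = σ²(1 − r̄), where r̄ = 2Σ(n−k)ρᵏ/[n(n−1)] and k runs from 1 to n−1. At ρ = 0.7, 1 − r̄ is 0.524 for n = 6 and 0.692 for n = 12, so the root ratio is √(0.692/0.524) = 1.15 before draw noise. Simulation of the full model (200,000 patients) gives these ratios of mean SD:

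| Weekly correlation | 12 vs 6 values | 12 vs 2 values |
|---|---|---|
| 0 | 1.03-1.04 | 1.24-1.25 |
| 0.3 | 1.06-1.07 | 1.38-1.41 |
| 0.7 | 1.13-1.16 | 1.59-1.70 |

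Against 8 values the excess is 1-8%. Equal blocks of 6 give 1.00. One value gives no SD.

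**4. Low-value counts.** Take median 1500, CV 30%, correlation 0.7 and no between-patient spread. The log-scale SD is √(ln 1.09 + ln 1.01) = 0.310, so P(ANC < 1000) = Φ(ln(1000/1500)/0.310) = Φ(−1.31) = 9.5%. Scheduled draws give 6 × 0.095 = 0.57 low values in the lead-in and 12 × 0.0955 = 1.15 per on-treatment interval: the count doubles, the share does not change. Adding triggered draws (simulated, trigger 1000, one redraw per new low episode, then twice weekly until recovery):

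| On-treatment interval | Low values per participant | Share of draws |
|---|---|---|
| Scheduled draws only | 1.15 | 9.5% |
| Plus triggered draws | 1.73 | 13.2% |
| Plus confirmatory redraws | 2.22 | 15.9% |

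Here the inflation is 2.22/1.15 = 1.9 fold. Over medians 1200-1800 and weekly correlations 0.3-0.7, counts inflate 1.4-2.1 fold (1.1-1.9 without redraws) and shares 1.2-1.8 fold (1.1-1.6). With the 1200 trigger, counts inflate 1.6-2.1 fold (1.3-2.0). If triggers already act from Visit 6, the on-treatment share is still about 1.0-1.5 times the lead-in share. At median 1800, CV 20% and correlation 0.3 the effect is trivial: 0.05 scheduled against 0.07 with all draws. Not modelled: daily draws below 500, twice-weekly draws in the first month for baseline 500-999, and the weekly option for participants who stay at 500-1000 beyond 4 weeks.

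**5. Selected baseline.** Same case (1500, 30%, 0.7), on the route with two values of at least 1000. With a two-value lead-in, the lead-in share below 1000 is 0% by construction, against about 9% on treatment, and the mean change is about −80 cells/mm³. With six values, any two of which qualify, the shares are 8.8% and 9.5%, and the mean change is about −5 to −8.

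**The case against.** The strongest reply is that little of consequence is affected. The three-month phase looks like a wrong duration that is easily corrected. For a full 6-week lead-in the SD effect is only 3-7% unless weekly correlation is high. The plan tests neither SDs nor low-value counts between periods; its formal comparison is mean change. The word weekly opens the sentence that contains the frequency clause, so limiting that clause to weekly values is a natural reading, and frequency can mean a proportion. Aim 1 and the first Aim 3 hypothesis speak of episodes, which repeat draws affect less. The ANC levels used above are assumptions: at a median of 2200 (CV 25%, correlation 0.5, between-patient CV 20%) there are only about 0.10 scheduled low values per participant per interval.

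Much of this stands. The outputs are descriptive, the size is uncertain, and the plan does not state that triggered draws are counted. What remains is that the first interval is not in the design, the frequency clause does not settle which draws enter, and episodes are not defined. The reply also does not cover short lead-ins, where even one scheduled draw per week leaves a baseline selected by the initiation rule.

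**Conclusion.** The point holds and should be fixed. The analysis names a baseline interval that contradicts the 6-week lead-in, and leaves open whether outcome-triggered draws count. Under the assumptions above, per-patient SDs look 3-16% higher on treatment for 12 against 6 values. If all draws are counted, on-treatment counts below 1000 are inflated about 1.4-2.1 fold at medians of 1200-1800, and trivially in absolute terms at higher medians or low variability.

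A reader might infer more than the documents support:

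- *That mean change is biased throughout.* With a near-full lead-in and scheduled draws, mean change and the low-value share are essentially unbiased; the baseline is only noisier. The bias of about −80 cells/mm³ belongs to two-value lead-ins on the main initiation route, in one assumed scenario.
- *That the SD distortion is typically 24-70%.* That range also applies only to two-value lead-ins, and the documents do not say how many participants will have one.
- *That the agranulocytosis limits are affected.* They count participants with the event, so neither the window nor repeat draws alters them.

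**What to change.** - In the analysis section, replace the three-month pre-treatment phase with the actual pre-clozapine window (scheduled 6 weeks), and reconcile the 9-month duration in STUDY DESIGN AND METHODS.
- Use one scheduled draw per week for means, SDs and the mixed model.
- Report low-ANC frequency per scheduled weekly draw, or per participant, by period. List triggered draws and confirmatory redraws separately for safety.
- Set a minimum number of lead-in values for a baseline SD and for any comparison of lead-in with on-treatment results. Report participants with shorter lead-ins separately or in a sensitivity analysis.
- Compare SDs only over equal numbers of weekly values, or through period-specific within-patient variances in the mixed model.
- The sponsor must reconcile the two thresholds for closer monitoring: 1000 in the MONITORING GUIDELINES table, and 1200 in the schedule footnote and in the section on WBC and infection monitoring. This review takes no view on which applies.

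The cost is minor wording and programming, with no new data. The summaries will use fewer values, and participants with very short lead-ins will have no baseline SD.
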